### **8.1.5.9 Assessment of Hypotonia**

The Investigator *or designee* will perform an assessment of hypotonia (head control and truncal stability) including absence or presence of hypotonia, severity grading, and changes since the last visit at the timepoints specified in the SoA (Section 1.3).

### **8.1.5.10 Children's Sleep Habit Questionnaire**

The *Children's Sleep Habit Questionnaire (CSHQ)*, which includes 45-items assessing sleep habits and possible difficulties with sleep, was developed for typically developing children aged 4 to 10 years (Owens et al 2000). The CSHQ will be administered to all participants in the study, irrespective of their chronological age. The CSHQ has previously been used outside of the standardized age norms to characterize the sleep parameters of children and adolescents with ASD aged 5 to 20 years (Schnapp et al 2022). The past week is the recall period, however if the last week is unusual for a specific reason, the most recent typical week will be chosen. Unless noted, "Always" refers to something occurring every night, "Usually" if it occurs 5 or 6 times a week, "Sometimes" if it occurs 2–4 times a week, "Rarely" if it occurs once a week, and "Never" if it occurs less than once a week. The questionnaire will be completed by the caregiver. Individual subscale scores as well as a total score can be calculated, with higher scores indicating more severe sleep disturbance.

### **8.1.5.11 Dup15q Syndrome Caregiver Global Impression of Severity and Caregiver Global Impression of Change**

The Dup15q CaGI-S is a nine domain, caregiver-rated measure, assessing the caregiver's impression of the impact of a participant's condition, in this case Dup15q syndrome (no other conditions/co-morbidities). This scale mirrors the Dup15q CGI-S described in Section 8.1.5.1. The nine concept-specific domains are seizures, non-verbal and verbal expressive communication, fine motor skills, gross motor skills, cognition, self-care, socialization, disruptive behavior, and sleep. The tenth domain is a score for overall severity. Guidelines will be provided to ensure consistency of rating.

The Dup15q CaGI-C is a 10-domain, caregiver-rated measure, assessing the caregiver's impression of change in the participant's condition, in this case Dup15q Syndrome (no other conditions or co-morbidities), compared with baseline. This scale includes the same domains as the Dup15q CaGI-S, and mirrors the Dup15q CGI-C described in Section 8.1.5.1. Guidelines for rating will be provided to ensure consistency of rating.

### **8.1.5.12 Wearable device**

Participants who are able to walk should wear a movement monitor during periods specified in the SoA in Section 1.3. All efforts should be made to ensure that participants who are able to walk 10 meters without assistance at screening and can tolerate the wearable device wear the device throughout the specified periods. The purpose of this device is to measure daily movement and activity levels of the participant accurately during normal daily living, outside of investigational site visits. The device consists of two sensors, one of which is worn on each ankle. As the device battery

requires recharging overnight, the device will not be worn at night. The device is *not* waterproof and *must not* be worn during bathing, swimming, or showering. The participant and caregiver will be trained on the correct use of the device, including correct fitting and wearing of the device, how to dock the device on the battery charging station, and when to return the wearable devices to the site. Detailed instructions as to use of the device are provided in the User Manual and Quick Start Guide.

#### **8.1.5.13 Palatability questionnaire**

Palatability will be indirectly assessed by asking caregivers about the child's reaction to the administration of the study treatment and ease of drug administration:

1. On the basis of the reaction/facial expression of your child, do you think that the medication is: pleasant, not sure, or unpleasant?
2. Do you sometimes have problems in giving the medication to your child because he/she refuses to take it or throws it up? Yes/No

#### **8.1.5.14 Caregiver Exit Interview**

If consent is provided, caregivers of study participants may be invited to participate in an optional, 1-hour, one-to-one interview, which will be recorded and transcribed. Interviews *will* be completed via telephone, in the caregiver's native language, and as soon as possible but no later than 4 weeks after the *Day 365 visit (during follow-up period if participant does not enter Part 2 or during the first 4 weeks of Part 2)*. Interviews are optional, and if a caregiver initially consents to participate in the interview, they can subsequently decide not to participate at a later time without any implications for their participation in the overall study. If a caregiver declines to participate at the start of the study this will not have any implication for the participation in the overall study.

These interviews will provide qualitative insights regarding among others: the daily life impact of Dup15q syndrome for the study participant; any key areas of change over the duration of the study; and the real-world impact of the changes that are most important. Caregivers will be asked to specifically consider areas such as developmental skills (including communication, motor function, cognition, behavior, and self-care), and seizures. Additionally, these interviews will capture information regarding how any change in Dup15q syndrome symptoms or functional ability may affect the daily life of the participant's caregivers and family. These interviews will *be performed by a trained interviewer independent of the site personnel to explore whether there were additional Dup15q syndrome concepts that were not captured in the standard efficacy assessments*. A semi-structured interview guide will be administered, including both open-ended and closed-ended questions.

## **8.2 SAFETY ASSESSMENTS**

Planned timepoints for all safety assessments are provided in the SoA (Section 1.3).

Safety assessments will consist of monitoring and recording AEs, including SAEs and AEs of special interest (AESIs); and measurement of protocol-specified safety laboratory assessments, vital signs, ECGs, seizure status, and other protocol-specified tests that are deemed critical to the safety evaluation of the study.

### **8.2.1 Medical History and Demographic Data**

Medical history includes lifetime clinically significant diseases, surgeries, cancer history (including prior cancer therapies and procedures), including infantile hypotonia and infantile spasms and date of diagnosis of Dup15q syndrome. *Medical history should be recorded in the eCRF.*

*The following information will also be collected and recorded in the eCRF:*

- All medications (e.g., prescription drugs, OTC drugs, herbal or homeopathic remedies, nutritional supplements)
- Non-pharmacological interventions, including e.g., behavioral, physical, or speech therapies, within 6 weeks prior to the screening visit
- Demographic data will include age, sex, and caregiver-reported race/ethnicity
- Level of education and participation in special educational or day programs

### **8.2.2 Physical Examinations**

A complete physical examination should include an evaluation of the head, eyes, ears, nose, throat, neck and lymph nodes, and the cardiovascular, dermatological, musculoskeletal, respiratory, gastrointestinal, genitourinary, and neurological systems.

Any abnormality identified at baseline should be recorded on the General Medical History and Baseline Conditions eCRF.

Weight, height and head circumference: Body weight (using calibrated scales) will be measured to the nearest 100 g at the timepoints specified in the SoA (Section 1.3). Head circumference will be measured in children below the age of 5 years to the nearest 0.1 cm using a flexible, non-stretchable tape.

*Abnormal* changes from baseline should be recorded in participant's notes. New or worsened clinically significant abnormalities should be recorded as AEs on the Adverse Event eCRF.

### **8.2.3 Tanner Staging**

Tanner staging for pubertal status will be determined at the timepoints listed in the SoA (Section 1.3). *In Part 1, Tanner staging will be assessed for participants aged 9 years or above at the time of signing the Informed Consent Form. In Part 2, Tanner staging will be assessed for participants aged 9 or above at the time of the assessment.*

*Tanner staging will not be performed after participants achieve Stage 5.*

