**Table 1 Schedule of Activities for Part 1 – Overview**

Period	Screening a	Baseline b	Treatment Period/Visit							Final Visit	Follow-up c, q	Early Termination c
Day	Day -35 to Day -2	Day -7 to Day -1	Day 1	Day 2	Day 14	Day 28 d	Day 92 c	Day 183 b	Day 274 c	Day 365 b	Day 395	Anytime
Weeks (approximate)	Week -5 to Week -1	Week -1	Week 1	Week 1	Week 2	Week 4	Week 14	Week 26	Week 40	Week 52	Week 56	
Visit window					± 5 days	± 5 days	± 7 days	± 7 days	± 7 days	± 7 days	± 10 days	
Assessments												
Informed consent	x									x t		
Inclusion/Exclusion criteria	x	x										
Caregiver expectation guidance u	x	x						x		x		
Randomization		x										
Demography	x											
Medical history	x											
Physical examination e	x	x						x		x		
Assessment of hypotonia		x		x	x			x		x		
Vital signs	x	x	x	x	x		x	x	x	x q	x	x
Genetic test : CMA r	x											
Genetic test : MS-MLPA r	x											
Genetic test: FISH r					x							
Pregnancy test f	x	x					x	x	x	x q	x	x
Urinalysis	x	x			x		x	x	x	x q	x	x
Hematology	x	x			x		x	x	x	x q	x	x
Clinical chemistry	x	x			x		x	x	x	x q	x	x
Coagulation	x											
Viral serology	x											
Thyroid hormones	x									x q		
RBR whole blood sample (optional)		x										
Tanner staging g		x								x		
12-lead ECG (triplicate)	x	x	x	x	x			x		x q		
Seizure status h		x				x	x	x	x	x	x	x
EEG monitoring i		x	x	x	x			x		x q		
Study drug administration j			◀							▶		
PK sample k			x	x	x		x	x	x	x q		x
Dup15q CGI-S h	x	x				x	x	x	x	x	x	x
Dup15q CGI-C h						x	x	x	x	x	x	x

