**Table 1 Schedule of Activities for Part 1 – Overview (cont.)**

o Assessed in participants aged 6 years and above at the time of signing the Informed Consent Form.

p [REDACTED]

[figure not shown]
q Only for participants who have either early terminated Part 1, or completed Part 1 but do not consent to enter the optional OLE.

r Genetic tests and associated samples are not mandatory assessments and do not need to be performed within the study in cases where the required genetic information is available in the patient's medical history.

s Optional exit interview, which should be performed within 4 weeks after the Day 365 visit (during the follow-up period if the participant does not enter Part 2 or during the first 4 weeks of Part 2), as applicable, will be performed by a trained interviewer independent of the site personnel. The exit interview can be performed whether or not the participant enters Part 2.

t Only for participants who enter Part 2 of the study. Should be signed before initiation of any activities at the Day 365 visit.

u The assessment should be done preferably before any other caregiver-reported assessments.

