**Table 3 Schedule of Activities for Part 2 (Optional Open-Label Extension) – Overview**

Period	Treatment Period/Visits					Follow-up a	Early Termination a
Day	Day 366	Day 457 b	Day 548 a	Day 730 a	Day 1095 a	Day 1125 (30 days after the final dose)	Anytime
Weeks (approximate)	Week 52	Week 65	Week 78	Week 104	Week 156	Week 160	
Year	1	1.25	1.5	2	3		
Visit window		± 7 days	± 7 days	± 7 days	± 7 days	± 10 days	
Assessments							
Caregiver expectation guidance c			x	x	x		
Physical examination			x	x	x	x	x
Vital signs	x		x	x	x	x	x
Pregnancy test d	x		x	x	x	x	x
Urinalysis	x		x	x	x	x	x
Hematology	x		x	x	x	x	x
Clinical chemistry	x		x	x	x	x	x
Coagulation	x						
Viral serology	x						
Thyroid hormones	x					x	x
Tanner staging e				x	x		
12-lead ECG (triplicate)	x		x	x	x	x	x
Seizure status f		x	x				
EEG monitoring g	x		x	x	x	x	
Study drug administration h	◀ ➡						
PK sample i	x		x	x	x		x
Dup15q CGI-S f		x	x	x	x	x	x
Dup15q CGI-C f		x	x	x	x	x	x

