### **8.2.8 Clinical Assessment of Suicidality**

*In Part 1, suicidality will be assessed for participants aged 6 years and above at the time of signing the Informed Consent Form. In Part 2, suicidality will be assessed for participants aged 6 years and above at the time of the assessment. The Investigator or designee will ask the caregiver of participants the following questions adapted from the C-CASA:*

- Suicidal ideation: Has the participant wished he/she were dead or wished they could go to sleep and not wake up?
- Suicidal behavior: Has the participant made a suicide attempt? Has the participant done anything to harm him or herself?
- Self-injurious behavior: Has the participant engaged in non-suicidal self-injurious behavior?

If the Investigator determines that any of these questions can be asked directly to the participant, based on the participant's ability to understand and to react to the questions, then those questions should be directed to the participant; if not, these should be directed to the caregiver. If the answer to any of these three questions is "yes", then the investigator will further evaluate the suicidal risk of the participant.

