### **9.3.3 Safety Analyses**

All safety analyses will be based on the safety analysis population. Safety endpoints will be described in appropriate summary tables and graphs. Individual outputs will be presented if required.

Descriptive summaries of exposure to study treatment will be prepared by treatment group (including treatment duration, total dose received, dose intensity).

Verbatim AE terms recorded in the eCRF will be mapped to MedDRA thesaurus terms. AE severity will be graded according to National Cancer Institute Common Terminology Criteria for AEs (v5.0). Data on AEs, SAEs, and deaths will be presented by treatment group in summary tables and in individual outputs, as appropriate.

Abnormal changes in EEG recordings compared to baseline will be presented in summaries and individual outputs with a focus on treatment-emergent epileptiform abnormalities. Seizure status as derived from the seizure diary entries by caregivers will be used to analyze changes from baseline in seizure types, frequency, and duration.

All clinical laboratory data will be stored on the database in the units in which they were reported. Laboratory test values will be presented in International System of Units (Système International d'Unités [SI] units;). Individual outputs will show flags for abnormal results. Summaries and shift tables will be prepared for selected laboratory tests to describe baseline and maximum post baseline severity grade.

Vital sign data will be presented *by individual listings* with flagging of values outside the normal ranges and flagging of abnormalities.

ECG data as well as data for height, weight, and head circumference will be presented using appropriate summaries and/or listings.

Suicidality questions adapted from the C-CASA will be analyzed descriptively in *participants aged 6 years and above*.

Tanner staging over time will be described in *participants from age 9*.

**Concomitant Medications:** The original terms recorded on the participants' eCRF by the Investigator for concomitant medications will be standardized by the Sponsor by utilizing a mapped term and appropriate drug dictionary level. Concomitant medications will be presented using appropriate outputs.

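### Part 1 sets eligibility for suicidality questions and Tanner staging by age at consent, so children who turn 6 in Part 1 are first asked about suicidality at Day 457 and children aged 6 to 8 at consent have no pre-drug Tanner stage

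*Combined protocol and SAP*

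**What the plan says.** **Tanner staging.** Section 8.2.3 sets the Part 1 rule: "In Part 1, Tanner staging will be assessed for participants aged 9 years or above at the time of signing the Informed Consent Form". It then sets another for the extension: "In Part 2, Tanner staging will be assessed for participants aged 9 or above at the time of the assessment". It also says "Tanner staging will not be performed after participants achieve Stage 5". Table 1 schedules staging at Baseline and Day 365. Table 3 schedules it at Day 730 and Day 1095, with nothing at Day 366.

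**Suicidality.** Section 8.2.8 states: "In Part 1, suicidality will be assessed for participants aged 6 years and above at the time of signing the Informed Consent Form". Table 1 footnote o agrees: "Assessed in participants aged 6 years and above at the time of signing the Informed Consent Form". For Part 2, Section 8.2.8 and Table 3 footnote m use age at the assessment. Table 1 schedules the questions at Screening, Baseline, Days 2, 28, 92, 183, 274 and 365, follow-up and early termination. In Table 3 the first scheduled visit with them is Day 457.

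**Endpoints and analysis.** Tables 5 and 6 list suicidality from age 6 and Tanner staging from age 9 without saying when age is taken. Section 9.3.3 does the same: "Tanner staging over time will be described in" participants from age 9, and suicidality in those aged 6 and above.

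**Status of the monitoring.** Section 8.3.8 says that suicidality monitoring is compulsory in trials of drugs acting on the CNS, and points to Section 8.2.8 for how it is done.

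**The concern.** Read on their own, the endpoint definitions cover any child who has reached 6 or 9 when assessed. In Part 1 the operating rule is narrower. The children left out are those who cross the threshold during treatment.

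For suicidality, a child who meets the stated age contributes no structured answer during the only randomized, blinded period, and has no pre-drug answer to compare with later. For Tanner staging, the children without a reference are those approaching puberty on treatment, and a pre-drug stage cannot be collected afterwards.

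**Working it through.** The documents state no count or share of affected children, so there is no plan figure to reproduce.

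**Step 1. What follows from the rules alone**

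Day 365 is about 1 year after Day 1, Day 730 about 2 years and Day 1095 about 3 years.

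| Age at consent | Suicidality in Part 1 | Tanner in Part 1 | Tanner in Part 2 |
|---|---|---|---|
| 5 | none, though essentially all are 6 by Day 365 | none | generally none |
| 6 | yes | none | Day 1095 only |
| 7 | yes | none | Day 730 and Day 1095 |
| 8 | yes | none, though essentially all are 9 by Day 365 | Day 730 and Day 1095 |
| 9 to 14 | yes | Baseline and Day 365 | Day 730 and Day 1095, until Stage 5 |

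The edges move slightly with the gap between consent and Day 1. Allowing 5 weeks for it changes the 35% in Step 3 to about 36%.

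A child aged 5 at consent who rolls over is first asked about suicidality at Day 457. That is 457 − 366 = 91 days into open-label drug, or about 15 months of basmisanil if randomized to it. A child aged 5 who does not roll over is never asked.

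A child aged 6 to 8 at consent is first staged after 1 to 3 years on basmisanil. This includes former placebo participants, who are not staged at Day 365 either.

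**Step 2. Assumed age mix**

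Inputs from Sections 4.1 and 9.1: about 90 randomized, at least about one-third aged 2 to 5, at most about one-fifth aged 12 to 14. Assumptions: these limits are the actual mix, ages are uniform within bands, and all 90 enter Part 2.

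- Aged 2 to 5: 90/3 = 30, so 30/4 = 7.5 per year of age
- Aged 12 to 14: 90/5 = 18
- Aged 6 to 11: 90 − 30 − 18 = 42, so 42/6 = 7 per year of age

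**Step 3. Results**

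- Aged 5 at consent: about 7.5 of 90. At 2:1, about 7.5 × 2/3 = 5 are on basmisanil. They are 7.5/(60 + 7.5) = 11% of children aged 6 or above by Day 365.
- Aged 6 to 8 at consent: 3 × 7 = 21. Aged 9 to 14: 60 − 21 = 39.
- Ever staged in Part 2 without a pre-drug stage: 21/60 = 35%.
- At Day 730 alone, only ages 7 and 8 count: 14/(14 + 39) = 26%.
- Within the 21, about 14 (ages 7 and 8) have two Part 2 stages and about 7 (age 6) have one.

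**Step 4. Range**

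| Assumed mix | Ever staged, no pre-drug stage | At Day 730 |
|---|---|---|
| Uniform from 2 to 14 | 3/9 = 33% | 2/8 = 25% |
| Half aged 2 to 5, one-fifth aged 12 to 14 | 13.5/45 = 30% | 9/40.5 = 22% |
| One-third aged 2 to 5, none aged 12 to 14 | 30/60 = 50% | 20/50 = 40% |

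At the enrolment limits, if 6-to-8-year-olds make up 40% to 60% of the 6-to-11 band, the ever-staged share runs from 28% to 42%. The Stage 5 stop can only raise it, because it removes older children who do have a Part 1 stage. Children aged 5 number about 7 under the uniform mix (90/13) and about 11 if half are aged 2 to 5 (45/4).

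**The case against.** The strongest reply is that nothing here is an error. Each rule is explicit and repeated consistently in the sections and footnotes, and the amendment rationale records the consent anchor as an intended clarification. A fixed age at consent gives every child assessed in Part 1 a Baseline value and a closed cohort, which is defensible in the randomized part. All of that stands. A reader might infer a contradiction between the two parts, or between Part 1 and the endpoint tables. The documents do not support that, because the endpoint tables are silent on the anchor and the operating sections supply it.

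A reader might also infer that change in Tanner stage cannot be computed for any child first staged in Part 2. That is too strong. Those aged 7 or 8 at consent still have a Day 730 to Day 1095 change. What they lack is the pre-drug reference.

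Other monitoring continues at every age. Adverse events are sought at each contact (Section 8.3.1). Suicidal behavior is a reason for discontinuation with no age limit (Section 7.1). The RBS-R, which has a self-injury subscale, is collected from Baseline to Day 365. Physical examinations include the genitourinary system (Section 8.2.2). So these children are not unmonitored; they are missing only the structured assessments. Both endpoints are descriptive in Part 1 and exploratory in Part 2, and Section 8.3.8 reports no suicidality signal from experience to date.

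Finally, Section 2.3.1.3 aims to keep direct evaluations of participants to the minimum needed. That weighs against extra pubertal examinations of young children. It carries little weight against a few questions that are normally put to the caregiver.

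**Conclusion.** The gap is real and follows from the rules without any assumption. Children who turn 6 in Part 1 are not asked the suicidality questions under blinded treatment, and children aged 6 to 8 at consent who are staged in Part 2 have no pre-drug Tanner stage. It is the consequence of a deliberate rule, and it does not touch the primary analysis, sample size or power.

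Its size rests on an assumed age mix. The shares also assume that entry to Part 2 does not depend on age, and the Part 2 counts assume full rollover. The figure of about one-third for Tanner staging is therefore not a property of the plan. It applies to children ever staged in Part 2, and is nearer a quarter at Day 730.

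The suicidality part justifies a change, because it only extends the protocol's own Part 2 rule to monitoring the protocol calls compulsory. The Tanner part is secondary and open to judgment.

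**What to change.** **Suicidality (recommended).** In Section 8.2.8 and Table 1 footnote o, set eligibility in Part 1 by age at the assessment, as in Part 2. State that anchor in the endpoint tables and Section 9.3.3. Report children who enter after Baseline separately, because they have no Baseline answer; that is the one downside. The cost is a wording change and a few questions, at contacts already scheduled, for about 7 to 8 children.

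**Tanner staging (optional).** For future enrollees, record a stage at the existing Baseline physical examination in children who will reach 9 during the study, that is, those aged about 6 or above at consent. Over a full enrolment of 90 this is at most about 21 extra stagings on the assumed mix, and fewer now that enrolment is under way.

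A Day 365 stage is a weaker substitute, since it is pre-drug only for former placebo participants. Of the 14 children aged 6 or 7 at consent, about 14 × 2/3 ≈ 9 would by then have had 52 weeks of basmisanil. A scheme with Baseline and Day 365 stages at age 8 plus a Day 365 stage at ages 6 and 7 would take 7 × 2 + 14 × 1 = 28 stagings in 21 children.

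The sponsor should weigh any added Tanner staging against the aim in Section 2.3.1.3 of limiting direct evaluations.
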